6.8.1.3 Supportive/sensitivity analyses

The same analysis as described in the main analysis section will be performed on the additional PD response endpoints: PD response[#] and PD response^{*}.

The main analysis will be repeated on the PPS, if the size of the PPS is less than 10% compared to the size of the FAS.

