10.1.7 Usage of the analysis sets

The PD analysis will be performed on the FAS based on the study treatment as randomized. Sensitivity analyses will be conducted using same endpoints as specified in Section 10.3 on the PPS.

Safety analyses will be performed on the SS based on actual study treatment received.

Subject listings will be based on the SS, unless otherwise specified. Subject disposition will be described for the Screened analysis set.

[Table 4](#) describes the analysis sets used for the analysis of each data set.

Table 4 Analysis datasets

Analysis	Screened set	RND	FAS	PPS	SS	PK set
Subject disposition	X					
Baseline and disease characteristics		(x)	X	(x)		
Previous and concomitant medication			X			
Study treatment exposure			X	(x)		
PD endpoints analyses			X	(x)		
Safety and tolerability analyses						X
PK data analysis						X

Note: Selected safety parameters, X: main analysis, (x): Sensitivity analysis to be conducted only if > 10% difference of set size with set used for main analysis.

FAS, Full analysis set; PD, Pharmacodynamic; PK, Pharmacokinetic; PPS, Per-protocol set; RND, Randomized set; SS, Safety set.

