4.2 Usage of the analysis sets

The analysis sets used for statistical analyses of specific variables are shown in [Table 2](#). Subject data listings were prepared using the SCR, unless otherwise specified.

Table 2 Analysis datasets usage

Analyses	Analysis sets					
	SCR	RND	FAS	PPS	SAF	PK set
Subject disposition	X					
Protocol deviations, analysis sets	X					
Demographics characteristics		(x)	X	(x)		
Medical history and current medical conditions			X			
Previous and concomitant medications			X			
Study treatment exposure			X	(x)	X	
Main (primary) PD endpoints			X	(x)		
Other PD endpoints			X			
Safety endpoints					X	
PK endpoints						X

X: main analysis, (x): Sensitivity analysis to be conducted only if > 10% difference of set size with set used for main analysis. FAS, Full analysis set; PD, pharmacodynamic(s); PK, pharmacokinetic(s); PPS, Per-protocol set, RND, Randomized analysis set; SAF, Safety analysis set; SCR, Screened analysis set.

The decision to perform a sensitivity analysis will be taken prior to any data unblinding, i.e., prior to database lock, during a blind data review.

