6.8.1 Primary pharmacodynamic endpoint

6.8.1.1 Variable

The primary PD endpoint is the *PD response* that is defined for each subject as a PRU < 100 starting 30 min after injection and lasting for at least 3 h, as measured via VerifyNow®.

The primary PD variable is the platelet reactivity as measured by VerifyNow® at each time point [see tables of assessments in the protocol: table 2 and table 3].

The analysis variable of the PD response is defined as follows for a given subject:

IF maximum of (PRU_{30m}, PRU_{1h}, PRU_{2h}, PRU_{4h}) < 100

AND (no more than 1 intermediate value (PRU_{1h} or PRU_{2h}) missing)

THEN PD response = YES

ELSE PD response = NO

Where PRU_{30m}, PRU_{1h}, PRU_{2h}, and PRU_{4h} refer to PRU measured by VerifyNow® at 30 minutes, 1, 2 and 4 hours after study drug administration. Time is based on planned time point and not on the actual collection time.

Supportive primary PD endpoint estimands

To assess robustness of results, two additional PD endpoints (estimands) will be defined for sensitivity analysis. The first endpoint, noted PD response[#], will be based on the same

algorithm as described above but using the actual collection time to define the following time windows:

Table 4 Time windows definitions

Collection time point (nominal) (time post study drug administration)	Time from PRU _{30m} (assessment of response, i.e., PRU < 100)	Time windows (~ 5% margin) (min. from study drug administration)
15 minutes	-	14 to 16
30 minutes	0	28 to 32
1 hour	30 minutes	57 to 63
2 hours	1.5 hours	114 to 126
3.5 hours*	3 hours	199 to 221
4 hours	3.5 hours	228 to 252
8 hours	7.5 hours	456 to 504
24 hours	23.5 hours	1368 to 1512

* no blood sample is taken at that time point, therefore no PRU value reported.
PRU, P2Y₁₂ reaction units.

The second endpoint, in the event of frequently missing PRU_{1h} or PRU_{2h} values, $\geq 10\%$ missing values overall, noted PD response*, will consider only the 30 minutes and 4 hours post study drug administration time points:

*IF maximum of (PRU_{30m}, PRU_{4h}) < 100
AND none of those values is missing
THEN PD response* = YES
ELSE PD response* = NO*

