11.3 Clarifications concerning endpoint definitions and related variables or statistical methods

Not applicable.

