Appendix B Protocol deviation list

The actual list of protocol deviation leading to exclusion from analysis set will be updated prior to study closure if required.

Table below provides the reason considered for excluding subjects from analysis set.

Table 7 Definition of exclusions from analysis sets

Analysis set	Reason for exclusion from analysis set	Programming conditions
Screened analysis set	Informed consent not initially obtained for the study	DV.DVREFID = IPD1D1
Randomized analysis set	Subject does not have a randomization number	Not in DS.RANDNO
Full analysis set	Subject did not get study treatment	EX.EXDOSE not >0
Safety set	Subject did not get study treatment	EX.EXDOSE not >0
Per-protocol set	Previous exposure to investigational drug	DV.DVREFID = IPD2A6
	Subject with platelet disorders at Screening	DV.DVREFID = IPD2A9
	Initiation or change in dose of oral P2Y12 during study	DV.DVREFID = IPD2D1
	Incorrect administration of study drug	DV.DVREFID = IPD2E1 or IPD3C1
	Deviation from study drug preparation instructions	DV.DVREFID = IPD2E2
	Incorrect blood sampling for platelet assays	DV.DVREFID = IPD2F2
	Background oral antiplatelet therapy not stable for 1 month prior to randomization	DV.DVREFID = IPD2A1
	Subject does not have stable coronary artery disease	DV.DVREFID = IPD2A3
	At least one post-dose VerifyNow® blood sample not evaluable (excluding the 24 h post dose)	at least one missing LB.LBSTRESN where LB.LBTESTCD= "P2Y12RU" and LB.LBTPT in (15 MIN POST-DOSE, 30 MIN POST-DOSE, 1 HOUR POST-DOSE, 2 HOURS POST-DOSE, 4 HOURS POST-DOSE, 8 HOURS POST-DOSE)
	Subject taking OATP1B1 and/or OATP1B3 inhibitor (systemic route) at Screening	DV.DVREFID = IPD2A7
PK analysis set	Subject has no plasma concentration measurement after administration of study treatment	all PC.PCSTRESC = « » when PC.PCTPT not PRE-DOSE

ICF, informed consent form; OATP, organic anion transporting polypeptide; PK, pharmacokinetic(s).

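### The size trigger for the per-protocol repeat in SAP 6.8.1.3 contradicts the rule in SAP Table 2 and protocol Table 4; secondarily, the LTA-PD response code omits the 8 h clause of its own definition

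*SAP*

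**What the plan says.** **Per-protocol trigger.** SAP 6.8.1.3 makes the per-protocol repeat conditional on size: it is done "if the size of the PPS is less than 10% compared to the size of the FAS". SAP 4.2, in the footnote to Table 2, marks the PPS analysis of the main PD endpoint as "Sensitivity analysis to be conducted only if > 10% difference of set size with set used for main analysis". The note to protocol Table 4 (section 10.1.7) gives the same condition: "Note: Selected safety parameters, X: main analysis, (x): Sensitivity analysis to be conducted only if > 10% difference of set size". The running text of protocol 10.1.7 also has a general sentence without a size condition: "Sensitivity analyses will be conducted using same endpoints as specified in Section 10.3 on the PPS".

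On timing, SAP 4.2 says: "The decision to perform a sensitivity analysis will be taken prior to any data unblinding", at a blind data review. SAP 11.1 declares one change from the protocol, to the 8 h PRU variable. SAP 11.3, headed "Clarifications concerning endpoint definitions and related variables or statistical methods", is marked as not applicable.

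**LTA-PD response.** SAP 6.8.2.1 defines this supportive variable in words as IPA-M of 50% or more from 30 min, sustained for 3 h or longer, with a limit at the eighth hour. The limit ends in a qualifier about subjects whose value is above, and its meaning is unclear. The algorithm in the same section returns YES when the 30 min and 4 h values are both present and both at least 50%, and NO otherwise.

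**The concern.** A per-protocol repeat is informative when the PPS differs materially from the FAS, and both tables say so. The sentence in 6.8.1.3 does not. Taken literally, it needs a PPS smaller than one tenth of the FAS. Taken as a statement about the difference, it runs the repeat when the two sets are nearly the same and omits it when they are not.

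6.8.1.3 is the section that specifies sensitivity analyses of the primary endpoint, so a programmer or a blind-review team would look there. A decision rule fixed before unblinding should have one version.

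For LTA, a subject can be coded as a responder while failing a clause of the written definition. Only a supportive binary variable is affected.

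**Working it through.** **Inputs.** Planned size is 324 (protocol 10.5). The FAS is all randomized and dosed subjects (SAP 4.1.3). Its actual size is unknown at planning, so 324 assumes that everyone is dosed; 310 and 300 are shown as alternatives. The PPS is a subset of the FAS, so any size difference is a loss.

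**The plan's own figure.** The one-sample test of 70% against 85%, two-sided 0.025, power 0.90:

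n = [(2.2414 × √0.21 + 1.2816 × √0.1275) / 0.15]² = 97.98, so 98 per arm. Then 98 × 1.10 = 107.8, so 108 per arm, and 3 × 108 = 324. This agrees with the protocol.

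**Three forms of the trigger**, with N = FAS size:

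- Tables: (N − PPS)/N > 0.10, i.e. PPS < 0.9N
- 6.8.1.3, literal: PPS < 0.1N
- 6.8.1.3, as a difference: (N − PPS)/N < 0.10, i.e. PPS > 0.9N

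For N = 324, 0.9N = 291.6 and 0.1N = 32.4.

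| FAS | Tables run it at | 6.8.1.3 literal | 6.8.1.3 as a difference |
|---|---|---|---|
| 324 | PPS ≤ 291 | PPS ≤ 32 | PPS ≥ 292 |
| 310 | PPS ≤ 278 | PPS ≤ 30 | PPS ≥ 280 |
| 300 | PPS ≤ 269 | PPS ≤ 29 | PPS ≥ 271 |

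Sample points for FAS 324:

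| PPS | Loss | Tables | Literal | Difference |
|---|---|---|---|---|
| 300 | 7.4% | no | no | yes |
| 291 | 10.2% | yes | no | no |
| 260 | 19.8% | yes | no | no |
| 162 | 50.0% | yes | no | no |
| 32 | 90.1% | yes | yes | no |

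For every PPS from 33 to 291 the tables call for the analysis and neither reading of 6.8.1.3 does. Under the difference reading the answer is the opposite of the tables at every size for N = 324.

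**LTA-PD response.** Take a made-up subject with IPA-M of 90% at 30 min, 85% at 4 h and 70% at 8 h. The code evaluates min(90, 85) = 85 ≥ 50 and returns YES. If the eighth-hour clause means that the effect must have ended by then, 70 ≥ 50 fails it. The code has no 8 h term, so it cannot tell this subject from one at 20%.

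**LTA sampling times.** Protocol Table 3 as extracted shows LTA ticks at pre-dose, 30 min, 1 h and 2 h, but its column alignment is not reliable. The same table puts the post-dose ECG under 2 h, where SAP 7.5 says 1 hour. Protocol 1.5.2 gives maximum single-day blood volumes of about 88 mL with LTA and 58 mL without, and protocol 3.2 gives 6 mL per LTA sample. (88 − 58)/6 = 5 samples, against four ticks. The volumes indicate a number of samples, not their times. If LTA were not taken at 4 h, the code would return NO for everyone; if not at 8 h, the clause could not be applied.

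**The case against.** The strongest reply is that this is an editorial slip. The two tables agree, the literal reading is absurd (at least 292 of 324 subjects excluded), and the likely intent is a PPS more than 10% smaller than the FAS. A competent review team would apply Table 2. That stands as to impact. It does not make the sentence correct, and a sentence that needs another section to reverse it should be reworded.

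Stronger readings that a reader might infer, and why they are not supported:

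- *There are three competing rules, because the sentence in protocol 10.1.7 is unconditional.* That sentence sits in the section that presents Table 4, and the Table 4 note supplies the condition. It is a general statement qualified by its own table.
- *The 10% point will probably be crossed.* SAP Table 7 does exclude a subject from the PPS for "At least one post-dose VerifyNow® blood sample not evaluable (excluding the 24 h post dose"), which covers six samples. If samples fail independently at rate q, the expected loss from this criterion is 1 − (1 − q)⁶: 5.9% at q = 1%, 11.4% at 2%, and 10% at q = 1.74%. If all six fail together, the 10% loss needs q = 10%. The documents give no failure rate, so crossing is possible but not shown to be likely.
- *The LTA code is wrong to count subjects below 50 kg, who have no LTA by design, as non-responders.* Protocol 10.3.2.2 counts undeterminable responses as non-responders in the main analysis, and protocol 10.3.2.4 carries the primary approach over to LTA. SAP 6.8.3 instead leaves undeterminable subjects out of the main response rate, without naming LTA. That conflict concerns the primary endpoint and is not an error of the LTA code.
- *The LTA code ignores values between 30 min and 4 h.* Whether any are scheduled cannot be settled from the extracted Table 3. If none are, two points are all there is.

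**Conclusion.** The trigger in SAP 6.8.1.3 is wrong as written, with high confidence: it contradicts SAP Table 2 and protocol Table 4, and section 11 does not declare a change. The cut-offs rest only on the assumed FAS size, and the pattern is the same at 324, 310 and 300. The effect is limited to whether one sensitivity analysis is run; no estimate, test or sample size for the FAS analysis changes.

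The missing 8 h term in the LTA-PD response is also certain from SAP 6.8.2.1 alone. What the clause requires is not, because its closing qualifier is unclear. The handling of subjects below 50 kg is an open question, to be settled together with the difference between protocol 10.3.2.2 and SAP 6.8.3.

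**What to change.** Before unblinding:

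1. Reword the condition in SAP 6.8.1.3 to: *if the PPS differs from the FAS by more than 10% in size*. Optionally add a line in SAP section 11 that the general PPS sentence in protocol 10.1.7 is subject to the Table 4 note.
2. Check the LTA sampling times in protocol Table 3 as issued. The code needs 4 h and the definition needs 8 h. Then either state what the eighth-hour clause means and code it, or delete it. Add intermediate LTA values to the rule only if that table schedules them.
3. When protocol 10.3.2.2 and SAP 6.8.3 are reconciled on undeterminable responses, state how subjects with no LTA by design are treated.

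The cost is one sentence, one optional line, and the text and derivation of one supportive variable. No new data are needed. Coding the 8 h clause as an end-of-effect condition could only lower the LTA responder rate.

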6.8.1.4 Subgroup analyses

The consistency of treatment effect across the following subgroups, as defined in protocol section 10.3.2.4, will be assessed by repeating the main analysis on primary PD endpoint, assuming there are enough subjects, i.e., ≥ 20 subjects by subgroup.

- Age: < 55 vs ≥ 55 years
- BMI: < 25.0 vs (≥ 25.0 and < 30.0) vs ≥ 30.0 kg/m^2
- Sex: male vs female
- Diabetes mellitus at baseline: yes vs no
- Chronic kidney disease: yes vs no

PTs to consider for identification of subjects with/without diabetes mellitus, or chronic kidney disease, are described in Section [5.4.4](#).

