10.3.2.4 Supportive/sensitivity analyses

The consistency across the following subgroups will be assessed by repeating the primary endpoint analysis, assuming there are a sufficient number of subjects:

1. Age: < 55 vs ≥ 55 years
2. Body mass index: < 25.0 vs (≥ 25.0 and < 30.0) vs ≥ 30.0 kg/m²
3. Sex: male vs female
4. Diabetes mellitus at baseline: yes vs no
5. Chronic kidney disease: yes vs no

An additional analysis of the supportive PD endpoint (LTA-PD response) will be conducted using the same approach as described for the primary PD analysis.

Further analyses will be described in the SAP as necessary.

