6.8.1.2 Analysis

The analyses described in this section consider the primary endpoint, i.e., PD response. Sensitivity analysis of the other estimands are described in the sensitivity analyses section.

Unless stated otherwise, all analyses will be conducted on the FAS.

The study is designed to demonstrate that at least one dose of ACT-246475 enables a large proportion (a target of 85%) of the randomized subjects to achieve a clinically meaningful level of IPA, defined as a PRU < 100.

Hypotheses and statistical model

The primary goal is to determine that the proportion (p) of subjects receiving a dose of ACT-246475, who achieve the PD response as measured by VerifyNow®, is statistically greater than 70%.

To achieve this objective, the testing strategy considers a sequential approach to demonstrate a statistically significant difference between the control arm (placebo) and at least 1 of the active arms, then to confirm that the observed response rate (P_r) in the same active arm is significantly statistically greater than the predefined response rate.

The comparison of each of the 2 active treatment arms will be conducted vs placebo, with the following hypotheses:

$$H_{p0_{HD}}: p_{placebo} = p_{HD} \quad \text{vs} \quad H_{p1_{HD}}: p_{placebo} \neq p_{HD}$$

$$H_{p0_{LD}}: p_{placebo} = p_{LD} \quad \text{vs} \quad H_{p1_{LD}}: p_{placebo} \neq p_{LD}$$

Where, $p_{placebo}$ is the proportion of responders in placebo arm, p_{HD} is the proportion of responders in the ACT-246475 16 mg arm and p_{LD} is the proportion of responders in the ACT-246475 8 mg arm.

Assuming either $H_{p0_{HD}}$, or $H_{p0_{LD}}$, or both are rejected, then the following hypotheses will be tested for each of the active doses that was statistically significantly different from placebo:

$$H_0: P_{responders} = 0.70 \quad \text{vs} \quad H_1: P_{responders} = 0.85.$$

Main analysis

The first set of null hypotheses ($H_{p0_{HD}}$ and $H_{p0_{LD}}$) will be tested each using a 2-sided z-test at an overall significance level (alpha) of 0.025, corresponding to an overall alpha level of 0.05 adjusted for multiplicity using the Bonferroni method.

Each of the second null hypotheses ($H_{0_{HD}}$ and $H_{0_{LD}}$) will be tested by a 1-sided z-test at an overall significance level (alpha) of 0.05 adjusted for multiplicity using the Bonferroni method, i.e., 0.025 for each comparison.

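### Subgroup consistency is assessed by repeating the main tests, which in small subgroups mostly reflect subgroup size; at about 6–7 per arm the test against 70% cannot reject

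*SAP*

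**What the plan says.** Protocol 10.3.2.4 lists five subgroup factors (age, BMI, sex, diabetes, chronic kidney disease). It says that consistency across them "will be assessed by repeating the primary endpoint analysis, assuming there are a sufficient number of subjects", and gives no number. SAP 6.8.1.4 keeps the approach: consistency of treatment effect "will be assessed by repeating the main analysis on primary PD endpoint, assuming there are enough subjects". It sets the entry condition: "assuming there are enough subjects, i.e., ≥ 20 subjects by subgroup". It does not say whether 20 is the subgroup total or a count per arm.

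The analysis to be repeated is in SAP 6.8.1.2. Each dose is compared with placebo by a 2-sided z-test at 0.025. For doses that pass, the response rate is compared with 70%; this second hypothesis "will be tested by a 1-sided z-test at an overall significance level (alpha) of 0.05", Bonferroni-adjusted, "i.e., 0.025 for each comparison". The same section also provides response proportions with 95% CIs by arm, a logistic regression of PD response and a mixed model for PRU. The mixed model carries a treatment × injection site term, whose stated purpose is to assess consistency of treatment effect across injection sites. No corresponding term is named for the five subgroup factors.

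**The concern.** Whether a test is significant in one subgroup and not in another depends on how many subjects each contains as well as on the effect. Consistency is a question about the difference between subgroups, and the plan specifies no estimate of that difference.

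Two features make this sharper here. The second test compares one active arm with a fixed 70% and ignores placebo, so a subgroup can pass or fail because of its background response rather than because of the drug. Also, the entry threshold is low enough that, on one reading, the second test has no possible positive result.

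At stake is the interpretation of a supportive analysis. The effect of age, sex and other covariates on PD is a stated objective (Protocol 2.2, SAP 3.3), and tables of repeated tests could be misread as evidence of heterogeneity.

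**Working it through.** **Inputs.** Null rate 70%, 1-sided 0.025 per dose, critical z = 1.960; dose vs placebo 2-sided 0.025, critical z = 2.241 (SAP 6.8.1.2). Allocation 2:2:2:2:1:1:1:1 with the placebo groups pooled, i.e. 1:1:1 (SAP 2.1, 8.1.1). Planning rate 85% against 70%, placebo 50%, 98 evaluable and 108 enrolled per arm (Protocol 10.5). Randomisation is stratified by baseline PRU only, so arm sizes within a subgroup vary by chance.

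**Which z-test.** The SAP does not give the variance form. The planned 98 per arm identifies it. With the null variance in the critical value:

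n = [2.241·√(0.7·0.3) + 1.282·√(0.85·0.15)]² / 0.15² = (1.0271 + 0.4576)² / 0.0225 = 97.98, i.e. 98.

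The Wald form gives 71 and does not reproduce the plan; it is also undefined at 100% response. The null-variance form is used below.

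**Best case for the test against 70%.** If every subject in the active arm responds, z = 0.30/√(0.21/n):

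| n in active arm | z | reaches 1.960? |
|---|---|---|
| 6 | 1.604 | no |
| 7 | 1.732 | no |
| 8 | 1.852 | no |
| 9 | 1.964 | yes |

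The minimum is 1.960²·0.21/0.09 = 8.96, so 9 in the arm, or about 27 per subgroup at 1:1:1. Twenty subjects in total give 20/3 ≈ 6.7 per arm.

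**Chance imbalance.** If each of 20 subjects falls in a given arm with probability 1/3, that arm has 9 or more with probability 0.19. Simulating this allocation, the chance per dose of passing the test against 70% is about 4% at a true 85% and about 19% at a true 100%. Passing both steps at 85% vs 50% is about 2%.

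**Power of the test against 70% at a true 85%** (binomial probability of the rejection region):

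| n in active arm | responders needed | power |
|---|---|---|
| 7 or 8 | none suffices | 0% |
| 15 | 14 | 32% |
| 20 | 19 | 18% |
| 30 | 26 | 52% |
| 54 | 45 | 71% |

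The dip at 20 is discreteness: 18/20 gives z = 1.95 and just misses. The 54 is half of a 108-subject arm, the best balance a two-level factor can have.

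**Power of dose vs placebo, 85% vs 50%** (pooled z-test, all outcomes enumerated): about 19% at 7 per arm, 43% at 15 and 96% at 54.

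With the same true rates in every subgroup, the chance of significance therefore runs from near zero to high purely with subgroup size.

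**The case against.** The strongest reply is that the section targets treatment effect, and the test of treatment effect is the placebo comparison, not the 70% threshold. That comparison has about 96% power in an evenly split arm, and it can reject at 7 per arm: 7/7 against 3/7 gives z = 2.37. This stands for large subgroups. It does not rescue small ones, where power is 19% at 7 and 43% at 15 per arm, and it is itself a reason not to repeat the threshold test.

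Second, consistency need not be read from tests alone. The repeated analysis gives proportions with 95% CIs and model estimates, the documents set no pass/fail rule for subgroups, and the study is labelled exploratory. This stands. A reader might infer that the planned output cannot answer the consistency question, or that a homogeneous effect is bound to look inconsistent. The documents support neither inference, because usable estimates will exist.

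Third, a reader might infer that the test against 70% can never pass at the entry threshold. That is too strong. It requires 20 to be a total and 8 or fewer subjects in the active arm. If 20 is per arm, 19 or 20 responders out of 20 would reject, though power at 85% is only about 18%. The documents give no expected subgroup sizes, so whether any listed level falls in the critical range of roughly 20 to 26 subjects is unknown.

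Fourth, the power figures depend on the assumed rate and variance form. At a true 90%, power at 54 per arm is 96% rather than 71%.

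**Conclusion.** The point holds in a limited form. Repeating the main tests is a poor gauge of consistency because the results largely track subgroup size, and the test against 70% is not a measure of treatment effect in any subgroup. On the total-count reading and at the planned allocation (6–7 per arm), that test cannot reject even if every subject responds; at least 9 in the active arm are needed. This rests on the null-variance z-test, inferred from the planned 98, and on the 85% and 50% planning rates for the power figures.

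The consequence is confined to supportive analyses in an exploratory study, estimates with CIs will be available, and the primary conclusion does not change. It is an optional improvement, at most a mild recommendation.

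**What to change.** In SAP 6.8.1.4:

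- Omit the test against 70% within subgroups.
- Present the difference from placebo with its 95% CI for each dose and subgroup level, as a forest plot.
- Add a treatment × subgroup interaction to the logistic model for PD response, one factor at a time, following the logic already used for injection site in the PRU mixed model. An ordinary logistic interaction has no finite estimate when a cell is all responders or all non-responders, so name a penalised (Firth) or exact method, or a risk-difference contrast, for sparse or separated cells.
- State whether the minimum of 20 applies per arm or in total, and give counts only below it.

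The cost is SAP wording, one model term per factor and one figure; no data collection changes. The downside is that interaction tests have low power at this sample size, so the reading will rest on the estimates and their CIs rather than on interaction p-values.
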